3. Patients who would not be suitable for a shunt
4. Patients whose condition is such that urgent surgical intervention is needed and time for enrolment is not available
5. Patients who are unable to give consent and there are no available next-of-kin

Sample size:

In order to detect a statistical significant difference ($p < 0.05$) between the two groups we would require 196 patients at. The power calculations were performed by our IT department at Leeds General Infirmary ([name]). This unit performs surgery for approximately 100 patients per year with shunt malfunction and we would therefore calculate that the study will take four years to complete assuming about half of patients will not be suitable for the study or will not wish to take part.

Randomisation process:

We intend to randomise half of our patients to each arm of the study (i.e. 100 will have a shunt revision for their treatment and 100 will have an ETV). This will be done by choosing from a collection of 200 identically sealed envelopes kept in the theatre suite. For obvious reasons the surgeon and patient cannot be blinded to the treatment to which they are randomised.

Consent procedures:

For each patient presenting with shunt malfunction, the surgeon will assess whether they are suitable for the study. Once suitability has been confirmed, consent will be sought in three possible ways:

1. In the case of a patient under 16: The parents of the child will be given an information sheet detailing the reasons for, aims and methods of the study. In the case of a child who has a normal conscious level and is of an age where he/she can understand the study rationale, there is a specific information sheet for the child. A consent form will be signed by the registrar or consultant taking consent and the parents of the child (and the child where appropriate). A separate information for children who can read will be provided.
2. In the case of a consenting adult, with a normal conscious level: Information on the study will be provided as above and written consent obtained by the attending registrar or consultant.
3. In the case of an adult with reduced conscious level or who is mentally unable to comprehend the study: Consent will be sought from the patient's next-of-kin. Where there is no next-of-kin available, the patient will be excluded from the study.

Study procedure:

Before recruitment to the trial:

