The patient who presents with symptoms or signs of shunt malfunction will have a thorough clinical examination, particularly neurological examination. Fundoscopy will be performed in all patients to ascertain the presence or absence of papilloedema. Where possible, a bedside visual field assessment and visual acuity test will be performed with a Snellen chart (competent older children and adults). Imaging will be performed as in all patients with suspected shunt malfunction:

- Shunt series of x-rays
- Cranial CT scan

These are not investigations exclusive to study patients but are performed routinely in such cases.

Where there is doubt as to the cause of the hydrocephalus or the suitability of the patient for ETV and the clinical condition of the patient allows the time a magnetic resonance imaging (MRI) study *may* be performed *prior* to consideration for study entry. This is done in most patients who have not had MR before as most patients presenting to us are assessed for suitability for ETV anyway. If the patient's condition is such that urgent surgery or other intervention is required, this intervention will take precedence over further investigation or entry into the study.

Once a patient is deemed suitable for trial, the patient/carer/parent/next-of-kin will be given information on the study and consent sought. Once written consent has been obtained, the patient is entered into the study. They will be given a study number and a proforma will be filled out. A sealed envelope will be opened to reveal the treatment arm and further consent for surgery will be obtained in the usual manner.

In the cases of those patients who present with shunt infection, they will not be considered eligible for the study until the infection has cleared. Treatment for shunt infection is by removal of the shunt, insertion of an external ventricular drain and administration of intravenous and intrathecal antibiotics for 10 days after the last positive CSF culture. Only at the point where a brand new shunt is considered would the patient be eligible for the study. Shunt infection is not a contraindication to ETV if infection is treated properly beforehand²³.

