Those that are randomised to shunt revision will have part or all of the shunt replaced. Patients randomised to the ETV arm of the study may have the malfunctioning shunt left in situ. Once the patient has had their surgery, they will be kept in hospital until they are deemed well enough for discharge home. There will be a visual assessment prior to discharge.

Follow-up will be arranged for 6 weeks, 6 months and one year for all study patients. At the 6 week and 6 month clinic the patient will have a cranial imaging to assess ventricular size. Those that have had an ETV will have an MRI scan to determine patency of the stoma as well (this is normal practice

following such a procedure). If a shunt revision is performed, a CT or MRI will be performed. Fundoscopy and visual acuity are also assessed in clinic. This is no different from the normal follow-up of a patient who has had treatment of a blocked shunt.

Should a patient make an unscheduled presentation because of symptoms related to their hydrocephalus or surgery and recurrence of the hydrocephalus is suspected they will be investigated in the usual manner in such cases (i.e. clinical and/or radiological confirmation of failure of shunt or ETV if that is the case).

A final proforma will be filled in at the patient's exit from the study. Exit from the study can happen in 3 ways:

- The patient represents with shunt/ETV failure
- The patient is well at one year following surgery with no need for further surgical intervention
- The patient voluntarily withdraws from the study for any reason at all

Duration of the study

Subject to R&D and ethics committee approval, enrolment into the study will commence on January 1st, 2007 and we would expect to enrol the 200th patient by December 31st, 2010. To ensure a minimum of one years-follow-up, data accrual will continue for one year after recruitment of the 200th patient. Overall we would expect this study to last at most 5 years.

Treatment efficacy assessment/endpoints:

In each patient the following endpoints will be assessed:

Primary endpoint:

One-year success rate of the procedure (one-year survival of shunt or ETV)

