- The procedure will be deemed a failure if the patient requires further surgical intervention within a year for treatment of their hydrocephalus. We felt that one-year follow-up was appropriate as most shunt and ETV failures occur in the first year following the procedure^{9,12}. The need for further surgery will be determined clinically or radiologically. In the case of patients who are in the ETV arm of the study, a sagittal MRI demonstrating the third ventricle floor will be sought where possible.

Secondary endpoints:

1. Occurrence of complications from surgery
2. Ventricular size changes
3. Length of inpatient stay
4. Number of re-attendances (excluding scheduled ones at 6 weeks, 3 months and 1 year) with symptoms related to their hydrocephalus/wound or implant.

Safety

Where either treatment would be deemed unsafe, the patient would be excluded from the study.

The risks of surgery are:

1. Death (less than 1% for shunt and ETV)
2. Epilepsy (approximately 5% short term risk in both treatments)
3. Minor vascular injury – Both treatments involve the passage of instruments through the brain to the ventricle. The risk of bleeding from this is about 5%. Most bleeds are sub clinical and don't result in neurological deficit. The risk of a bleed causing a deficit is about 1-2% for both treatments
4. Major vascular injury: This is a risk with ETV where basilar artery injury has occurred - death from it has been reported¹. However, most large series of patients treated with ETV, report no such injuries.
5. Infection: The shunt infection rate in this unit at present is 5%. The rate of CSF infection or ventriculitis is 0-10% in large series^{8,11,21} The rate of infection
6. CSF wound leak: This occurs in up to 5% of newly implanted shunt and is a high risk factor for infection. In the case of ETV it usually means that the ETV will not work and a shunt is needed²¹
7. Overdrainage and slit ventricle syndrome. This is a rare but serious problem in children treated with shunts. It can cause severe headaches and often requires further shunt surgery. It is not a recognised complication of ETV²²
8. Subdural haematomas. This is a complication seen with overdrainage of shunts in adults. It can mean that a patient will require surgery to remove the haematomas and shunt revision. It is also rarely seen with ETVs.

Subject withdrawal

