Obviously, a patient or family can withdraw from the study at any point. If they withdraw at any point before the one-year follow-up, they will be excluded from analysis at the end of the study.

Is endoscopic third ventriculostomy an effective treatment in patients with hydrocephalus and cerebrospinal fluid shunt malfunction?

Data recording and proformas

All data will be recorded prospectively on proformas by one of the investigators:

There will be a proforma for

- The initial inpatient admission, surgery and discharge
- Follow-up proforma to be filled in at one year or earlier if treatment fails

Data storage:

All proformas will be kept in paper form by the principle investigator in his office and will be transferred onto a computer database on one desktop PC in the department of neurosurgery. This will be password controlled and only the named investigators will have access to it

ETV vs. Shunt Revision Study: admission

Hospital number 1

Surname First name Date of birth Date of entry into study

Admission details

Date of admission
 
Mode of presentation
 
 Self referral
 
 Through OPD
 
 GP
 
 Other hospital
 
 A&E
 
 Other...
	
Cause of hydrocephalus
 
 IVH
 
 Aqueduct stenosis
 
 Myelomeningocele
 
 Chiari malformation
 
 Tumour
 
 CSF infection
 
 Head injury
 
 Dandy Walker
 
 Craniosynostosis
 
 Venous thrombosis
 
 Unknown
 
 Other

---	---

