- ventricle size decreased (still large)
- ventricle size unchanged (normal)
- ventricle size unchanged (still large)
- ventricle size increased
- Other...

MRI

- not done
- ventricle size decreased (normal)
- ventricle size decreased (still large)
- ventricle size unchanged (normal)
- ventricle size unchanged (still large)
- ventricle size increased
- flow through stoma (if ETV)
- Other...

Number of visits post discharge

Complications post-op	Free text
-----------------------	-----------

Status

- Functioning at one year
- Failed before one year
- Dead
- Lost to follow-up

Symptoms in successful patients

- none
- mild
- severe (requiring admissions)

Where failed: Date of failure

- Operation for failure
- shunt
 - ETV again
 - Other...

Cause of failure Free text

Statistical considerations:

The primary endpoints will be compared by a chi-squared test comparing success rates at one year in each group.

The timing of failure in those treatments that do fail will be compared using the Kaplan-Meier survival curves.

Complication rates are expected to be small and we expect no statistical difference in a study this size.

Mean numbers of reattendances and mean reduction in ventricular size will be compared using student's t-test

Data storage

All data will be stored on a PC and in paper form in the neurosurgical department.

Patients will be identified by their hospital numbers and only neurosurgical medical staff will have access to the data

Ethical considerations

There are no specific ethical issues in this study. Both treatments are well-recognised alternatives for managing patients with hydrocephalus

Publication of study findings

We plan to publish the results of this study in Journal of Neurosurgery

Presentations of the data will be made to at academic meetings (e.g. European Society for Pediatric neurosurgery and/or the International Society for Pediatric Neurosurgery)

2. Barlow P: Indications for endoscopic third ventriculostomy: a review of successful and failed cases. **British Journal of Neurosurgery** **11**:456, 1998

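### Patients who withdraw before one year are dropped from the analysis, so the primary test compares completers rather than the randomised groups

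*Protocol*

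**What the plan says.** Five parts of the protocol bear on this.

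- **Subject withdrawal** sets the analysis rule: "If they withdraw at any point before the one-year follow-up, they will be excluded from analysis at the end of the study".
- **Study procedure** fixes the order of events. Trial consent comes first: "Once written consent has been obtained, the patient is entered into the study". Allocation and surgical consent follow: "A sealed envelope will be opened to reveal the treatment arm and further consent for surgery will be obtained in the usual manner". The same section lists three ways to leave the study: failure of the shunt or ETV, being well at a year without further surgery, or this one: "The patient voluntarily withdraws from the study for any reason at all".
- **Randomisation process** confirms the open design: "For obvious reasons the surgeon and patient cannot be blinded to the treatment to which they are randomised".
- **Treatment efficacy assessment/endpoints** defines the primary outcome: "The procedure will be deemed a failure if the patient requires further surgical intervention within a year for treatment of their hydrocephalus".
- **Statistical considerations** names the primary test: "The primary endpoints will be compared by a chi-squared test comparing success rates at one year in each group". It also plans Kaplan-Meier curves for the timing of failure.

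Nothing in the protocol keeps withdrawn patients in the analysis, uses their follow-up to the date they left, or provides a sensitivity analysis for their absence.

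**The concern.** The rule removes randomised patients because of something that happens after randomisation. A patient who leaves event-free at month 11 is removed as completely as one who leaves on the day the envelope is opened.

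Removal is harmless to the estimate if, in each arm, those who leave have the same chance of success as those who stay. The design gives no assurance of this. Patients learn their arm while they can still decline to continue, they know throughout the year which procedure they had, and their reasons for leaving are unrestricted. Both the number who leave and their prognosis can therefore differ between arms.

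The stated objective is to find which group is more likely to need further surgery within a year. Under this rule the primary test answers that question only for those who stayed.

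**Working it through.** **Inputs from the protocol**

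- Shunt revision, one-year success: 108 revisions in 2004, of which 47 needed a further procedure. (108 - 47)/108 = 61/108 = 56.5%, which reproduces the background figure.
- ETV success in the cited retrospective series: 70%. The gap between the two background rates is 70 - 56.5 = 13.5 points.
- Stated sample size 196 with equal allocation: 196/2 = 98 per arm.
- Withdrawal after randomisation: no rate is given. The values of 5% to 20% below are assumptions.

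**Formula.** Let p be the true success rate in an arm, w the fraction of that arm excluded, and s the proportion of those excluded who would have succeeded. Success among those kept is (p - w·s)/(1 - w), so the shift in that arm is

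shift = w(p - s)/(1 - w).

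It is zero only if w = 0 or s = p. It does not depend on the number of patients.

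**Illustration with no true difference.** Set p = 0.565 in both arms and exclude patients from the ETV arm only. At w = 0.10:

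- all would have failed (s = 0): 0.10 × 0.565/0.90 = +6.3 points
- two thirds would have failed (s = 1/3): 0.10 × (0.565 - 0.333)/0.90 = +2.6 points
- all would have succeeded (s = 1): 0.10 × (0.565 - 1)/0.90 = -4.8 points

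The chance of a false significant result uses the two-sided pooled z-test, which is equivalent to the chi-squared test: Φ((d - 1.96·se0)/se1) + Φ((-d - 1.96·se0)/se1). Here d is the false difference, se0 the pooled standard error and se1 the unpooled one. For w = 0.10 and s = 0, the analysed numbers are 88.2 and 98, d = 0.0628, se0 = 0.0721 and se1 = 0.0718, giving 0.137 + 0.002 = 14%.

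False difference in points, with type I error in brackets:

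| ETV arm excluded | All would have failed | Two thirds would have failed | All would have succeeded |
|---|---|---|---|
| 5% | +3.0 (7%) | +1.2 (5%) | -2.3 (6%) |
| 10% | +6.3 (14%) | +2.6 (6%) | -4.8 (10%) |
| 15% | +10.0 (28%) | +4.1 (9%) | -7.7 (18%) |
| 20% | +14.1 (49%) | +5.8 (12%) | -10.9 (30%) |

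Keeping all randomised patients with their outcomes gives 0 points and 5%.

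**Equal withdrawal rates do not protect.** If 10% leave each arm, but the ETV leavers would all have failed and the shunt leavers are representative, the false difference is still +6.3 points, with type I error again about 14%.

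**The case against.** The best defence has four parts.

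1. *A confirmed failure is a separate, counted exit.* Symptomatic patients who return are investigated and recorded as failures, which limits how many failures can disappear as withdrawals. This stands and makes the all-failures column an extreme. It does not cover patients who leave before a failure is recorded.

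2. *Patients consent to the trial before the envelope is opened*, so they have already accepted either arm, and the protocol does not say that declining the allocated operation counts as withdrawal. This also stands. That such refusals would be deleted is an inference. But nothing prevents a patient from withdrawing on learning the arm, and the exclusion rule would then apply.

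3. *Size and direction are assumed.* True. In the moderate case (10% excluded, two thirds failures) type I error is only about 6%, and the sign reverses if would-be successes leave. A reader might infer that success is overstated in the arm with more withdrawals, but the protocol contains nothing on who leaves or why.

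4. *A statistical analysis plan could settle it.* Not here: a plan that analysed all randomised patients would contradict the protocol's sentence.

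Three stronger readings are not supported.

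- A reader might take the Safety sentence, "Where either treatment would be deemed unsafe, the patient would be excluded from the study", to remove ETVs abandoned during surgery. It covers both treatments and reads most naturally as eligibility screening, which the protocol places before consent and allocation.
- A reader might infer that a fatal complication counts as a success. It meets neither definition: success at exit requires being well at a year, and the follow-up form records death apart from a functioning procedure. Its classification is simply open, and the protocol puts mortality below 1% for both procedures.
- A reader might argue from the narrow margin between 200 envelopes and 196 patients. That concerns sample size; the bias above does not depend on it.

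**Conclusion.** The rule is wrong as written. It is an explicit instruction, it governs the primary comparison, and no other part of the protocol repairs it. Followed literally, it turns a randomised comparison into one of completers.

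What is established is that bias is possible, not how large it is. Under the assumptions of no true difference, 56.5% success, 98 per arm and 10% of the ETV arm excluded, the shift runs from -4.8 to +6.3 points. The upper end is nearly half of the 13.5-point gap between the protocol's background rates (6.3/13.5 = 47%). With few withdrawals, or withdrawals unrelated to outcome, the effect would be small or nil. Because the direction cannot be known in advance, the result could not be called conservative for either procedure.

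The treatment of death without reoperation is a minor gap: death is not among the listed exits, and the primary endpoint does not say how it counts.

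**What to change.** Replace the exclusion sentence under Subject withdrawal with wording such as:

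> All randomised patients are analysed in the arm allocated. For patients who withdraw or are lost, one-year reoperation status is taken from hospital records unless consent to use data is withdrawn. Data up to withdrawal are kept, and the Kaplan-Meier curves censor at last contact only where status cannot be obtained. The chi-squared comparison of one-year success is kept, with best-case/worst-case sensitivity analyses for outcomes still missing and the completers-only result as a further sensitivity analysis.

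Add one sentence to the primary endpoint stating how death without reoperation is counted.

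Retrieval of outcomes must come before censoring, because censoring alone does not cure withdrawal related to prognosis. Suppose 70 of 100 ETV patients would succeed, and 10 leave at allocation, of whom 6 would have failed. Censoring those 10 at time zero still gives (70 - 4)/(100 - 10) = 66/90 = 73.3%, the same answer as deleting them.

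The cost is some record retrieval and slightly more analysis. It looks feasible: this is a single centre and patients are identified by hospital number. Reoperation elsewhere could be missed, which is one reason for the best-case/worst-case bounds. The primary test does not change.

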the subarachnoid space can allow CSF to bypass an obstruction, thus obviating the need for a VP shunt. The use of endoscopic third ventriculostomy (ETV) is now becoming more prevalent in the primary treatment of hydrocephalus particularly in cases of obstruction and a consensus of opinion exists regarding their high likelihood of success in these cases¹³. The use of ETV is also gaining popularity in the treatment of shunt malfunction even in cases where there was a communicating hydrocephalus to begin with. There are several papers advocating this (secondary ETV) as a worthwhile alternative to shunt revision. In some cases particularly in older patients ETV has been suggested as a treatment for shunt blockage in patients whose hydrocephalus was originally communicating^{3,5,7,9,20,25}.

In this unit we perform approximately 100 shunt revisions per year. In 2004, we performed 108 shunt revisions. In 47 of those cases (43.5%), a further procedure was needed because of complications with the new shunt. The 1-year survival revised shunts in 2004 was therefore 56.5%. There are series which show higher success rates (70%) with ETV following shunt failure²⁰. These are retrospective.

To date there has been no prospective analysis comparing ETV to shunt revision in patients who present with shunt problems requiring surgery.

Study objective:

The aim of this study is to compare the success rates of ETV and shunt revision in the treatment of shunt malfunction in patients with hydrocephalus, In other words to:

- determine which group of patients are most likely to require further surgery within a one year follow-up period
- To compare immediate complication rates between the two patient groups

Sample population:

All patients presenting to Leeds General Infirmary with shunt obstruction will be considered for the study regardless of the original cause of their hydrocephalus.

Inclusion criteria:

1. Symptoms/signs or radiological evidence of shunt obstruction
2. Ventricular anatomy making an endoscopic procedure feasible as judged by the attending consultant neurosurgeon:
 - a. Lateral and third ventricles adequate size
 - b. Thin third ventricle floor
 - c. Adequate pre-pontine cistern to fenestrate into with an endoscope
3. Age greater than one year

Exclusion criteria

1. Age less than one year (these children are less likely to benefit from ETV^{2,6,14-16,18,23,24})
2. Small ventricles preventing passage of the endoscope

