
Date of first shunt insertion
 
Date of last shunt revision
 
Number of previous revisions
 
Previous ETV? 
 
Site of ventricular catheter
 
 Frontal
 
 Parietal
 
 Occipital
 
 Other...
	
Type of shunt: Valve
 
Proximal catheter
 
Distal catheter
 
Antisiphon device  None  Integral  Separate
 
Rickham reservoir  None  Integral  Separate
 
Site of peritoneal catheter
 
 peritoneum
 
 heart
 
 pleura
 
 Other...

---	--

Symptoms
 
 Headache
 
 Nausea/Vomiting
 
 Irritability
 
 Lethargy
	
 New or changed seizures
 
 Diplopia
 
 Fever
 
 Developmental delay
	
 Deteriorating performance
 
 Abdominal symptoms
 
 Other...

--	--	---

Signs
 
 Fever
 
 Papilloedema
 
 Bulging fontanelle
 
 Increasing head circumference
 
 Decreased L.O.C.
 
 Nuchal rigidity
	
 Cranial nerve palsy
 
 Parinauds/Sunseting
 
 Focal deficit
 
 CSF leak
 
 Shunt reservoir not refilling
 
 Erythema over shunt
	
 Skin erosion/discharge
 
 Abdominal mass
 
 Peritonitis
 
 Delayed development
 
 Other...

---	--	--

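### The primary analysis is fixed as an unadjusted chi-squared test in a population mixed by cause and age: valid, but it leaves a modest amount of precision unused

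*Protocol*

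**What the plan says.** The Statistical considerations section of the protocol commits to one primary analysis: "The primary endpoints will be compared by a chi-squared test comparing success rates at one year in each group". It names no baseline factor. The Randomisation process section describes drawing from 200 sealed envelopes and mentions no stratification.

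The population is broad. Under Sample population, patients with shunt obstruction "will be considered for the study regardless of the original cause of their hydrocephalus", and the only age limit is one year.

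The introductory text divides hydrocephalus into obstructive and communicating types. On ETV as primary treatment, it says that use is growing "particularly in cases of obstruction and a consensus of opinion exists regarding their high likelihood of success in these cases". It adds that secondary ETV has been suggested for blocked shunts in originally communicating cases, especially in older patients. The exclusion criteria say that children under one year are less likely to benefit.

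The admission form records date of birth, a checklist of causes, and "Number of previous revisions". None of these enters the primary analysis.

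**The concern.** Neither the design nor the primary analysis takes account of case mix, although the protocol treats cause as relevant to whether ETV works. Two things follow.

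- **Precision.** If cause predicts one-year success, an analysis that conditions on it gives a tighter estimate from the same patients. It also absorbs chance imbalance between arms, which simple randomisation of about 200 patients will produce fairly often.
- **Interpretation.** A pooled difference can describe neither type of patient well. Suppose ETV succeeded in 85% of obstructive and 55% of communicating cases, in equal numbers, and shunt revision in 56.5% of both. The true differences would be 85 − 56.5 = +28.5 points and 55 − 56.5 = −1.5 points. The planned test would be looking at their average, (28.5 − 1.5)/2 = +13.5. A split by cause chosen after the data are seen would carry little weight.

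**Working it through.** **Inputs from the protocol**
- Shunt revision: "The 1-year survival revised shunts in 2004 was therefore 56.5" per cent.
- ETV: "There are series which show higher success rates (70%) with ETV following shunt failure". This is background, not a named design assumption.
- Significance level 0.05, taken as two-sided; the protocol does not say.
- Sample size: "we would require 196 patients at", used as a total (about 100 per arm planned). No power is stated in the text available.

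**Assumptions, because the protocol gives no prognostic effect sizes**
- One binary cause factor present in half of the patients.
- A range of effects of that factor on success.

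**1. The protocol's own figure.** The pooled-variance formula for 56.5% versus 70% at 80% power is n per arm = [1.960·√(2·0.6325·0.3675) + 0.842·√(0.565·0.435 + 0.70·0.30)]² / 0.135². This is (1.336 + 0.568)² / 0.018225, or 200 per arm after rounding up (400 in total). So 196 is not reproduced as a total, though as a per-arm number it is close. With 98 per arm, two-sided power is 50%. That is the baseline for what follows.

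**2. Validity of the planned test.** In simulations of 20,000 trials per scenario at 98 per arm, with the factor's odds ratio from 1 to 9, type I error was 4.9% to 5.3% for both the chi-squared test and a Cochran-Mantel-Haenszel test stratified on the factor.

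**3. Chance imbalance.**
- The SD of the between-arm difference in a 50% factor at 100 per arm is √(2·0.25/100) = 7.1 points.
- If the factor moves success by 25 to 30 points, one SD of imbalance shifts the crude difference by 0.071·25 = 1.8 to 0.071·30 = 2.1 points.
- For comparison, the standard error of the crude difference is √[(0.565·0.435 + 0.70·0.30)/100] = 6.8 points.
- At 98 per arm an imbalance of 10 points or more has z = 0.10/√(0.5/98) = 1.40, so it occurs in about 16% of trials.

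**4. Variance removed by adjustment.**
- *Cause acts equally in both arms.* Success of 80% versus 50%: (0.30/2)² / (0.65·0.35) = 0.0225/0.2275 = 9.9%. Success of 75% versus 50%: (0.25/2)² / (0.625·0.375) = 0.0156/0.2344 = 6.7%. Out of 200 patients this is worth about 13 to 20.
- *Cause acts only under ETV, with shunt revision flat at 56.5%.* For 80% versus 50%: (0.30²·0.25/2) / (0.2275 + 0.2458) = 0.01125/0.4733 = 2.4%. For 75% versus 50%: 0.0078/0.4801 = 1.6%. This is worth about 3 to 5 patients.

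**5. Power, unadjusted versus stratified on cause (98 per arm, overall rates 56.5% and 70%)**

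| Assumed effect of cause | Chi-squared | Stratified |
|---|---|---|
| 25-point gap, both arms | 50% | 53% |
| 30-point gap, both arms | 50% | 54% |
| ETV arm only (85% vs 55%) | 49% | 51% |
| Odds ratio 2 | 50% | 51% |
| Odds ratio 3 | 50% | 53% |
| Odds ratio 5 | 50% | 56% |
| Odds ratio 9 | 49% | 60% |

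The last two rows need a stronger factor than anything in the protocol suggests.

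**6. Is the covariate on the form?** Cause is recorded as a list of aetiologies, with Unknown and Other as options. Obstructive versus communicating is not a field. The introductory classification puts haemorrhage and infection under both types, so the list does not map to two groups without a rule. The CT and MRI items on aqueduct patency and fourth-ventricle size can help.

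**The case against.** The strongest objection is that nothing here is an error. A chi-squared test of one-year success is valid in a 1:1 randomised comparison, and the shift of about 2 points from chance imbalance is already part of its standard error. Covariates, intervals and subgroup analyses are also commonly left to a statistical analysis plan, which may exist. Both points stand. The absence of an interval or an interaction test is therefore not raised as a fault. What remains is narrower: the protocol does fix the primary test, and the test it fixes uses no baseline information.

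Four stronger readings are tempting, and the document supports none of them.

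- **That strong prognostic factors are being ignored.** Support for cause is qualitative and concerns ETV as primary treatment. Lower benefit by age is stated only for under-ones, who are excluded. Nothing says that revision history predicts outcome; it is merely recorded.
- **That the gain is worth 13 to 20 patients.** This needs the same effect of cause in both arms, whereas the protocol's evidence concerns ETV only. On that basis the gain is about 3 to 5 patients.
- **That the pooled result hides harm in communicating cases.** No rates by cause are given, so this is conjecture. An interaction in about 200 patients would be too imprecise to settle it.
- **That the change is analysis wording only.** A classification rule has to be written and applied.

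**Conclusion.** The point holds as an efficiency improvement, not as an error or a source of bias. The protocol fixes an unadjusted primary test in a population mixed by cause and age, while collecting cause and date of birth. Under the illustrative assumptions (a factor present in half of the patients, a gap of 25 to 30 points in both arms or 30 points in the ETV arm only, 98 per arm), the power forgone is about 1 to 4 points. It would be larger only if cause were a much stronger predictor than the protocol indicates. Adjustment is worth making because it uses data already being gathered and because a cause grouping chosen in advance is more credible than one chosen later.

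It would be wrong to infer that adjustment rescues the trial's power. With 196 as a total, power for the protocol's own rates stays near 50% with or without it.

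**What to change.** 1. Make the primary estimate a risk difference in one-year success with 95% CI, adjusted for cause group and age, either standardised from a logistic model or by a stratified analysis. State in advance how age is entered. Standardisation targets the same overall difference as the crude comparison.
2. Keep the chi-squared test as the unadjusted result.
3. Before outcomes are known, fix a rule that maps the admission form's cause list to obstructive, communicating or unclear. It should say how haemorrhage and infection are classified and may use the baseline CT and MRI items.
4. Treat number of previous revisions as an optional covariate.
5. Report the effect by cause group with intervals, labelled descriptive.

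The cost is writing and applying the mapping rule, plus slightly more analysis. No extra patients or visits are needed. The sample size needs its own correction.
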